## **2. TYPE OF PLANNED ANALYSIS**

### **2.1. EMEA 120-Day Response and AASLD Analysis**

After all group 1 and group 3 subjects (group 1: genotype 2/3 treatment-naive subjects, SOF+RBV 12 weeks; group 3: genotype 1 treatment-naive subjects, SOF+RBV 24 weeks) have completed the posttreatment Week 12 visit or prematurely discontinued from study, an analysis will be conducted on key safety and efficacy data for all treatment groups to be included in the 120-day EMEA response and AASLD analysis to support the NDA of SOF for use in combination with other agents for the treatment of CHC in adults.

The last visit date for the posttreatment week 12 visit for group 1 and group 3 subjects (defined as LPLV date) is approximately September 9, 2013. The database finalization date for this analysis is approximately September 30, 2013.

All safety and efficacy eCRF data collected up to the LPLV date specified above will be cleaned and included in the analysis. Data between LPLV date and database finalization date will be included in the database, but may or may not be cleaned and/or reconciled.

### **3. GENERAL CONSIDERATIONS FOR DATA ANALYSES**

#### **3.1. Analysis Sets**

Analysis sets define which subjects are included in an analysis. A summary of the number and percentage of subjects in each analysis set will be provided by treatment group and in total as part of the subject disposition summary.

##### **3.1.1. Full Analysis Set**

The full analysis set (FAS) includes the following subjects who were enrolled into the study and received at least one dose of study drug:

- Treatment-naive subjects with genotype 1, 2 or 3 HCV infection
- Treatment-experienced subjects with genotype 2 or 3 infection who have completed the posttreatment Week 12 visit or prematurely discontinued from study

The study drugs in this study include SOF and RBV. Efficacy analysis of antiviral activity will be based on FAS.

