## 6. STUDY PROCEDURES

All subjects will complete screening, on-treatment and post-treatment assessments. All subjects will complete a 4-week Post-Treatment visit regardless of the treatment duration. Subjects with HCV RNA < LLOQ at the end of treatment and 4-Week Post-Treatment visit will complete 12-week and 24-week Post-Treatment visits unless confirmed viral relapse occurs. Completion of the study will occur at the 24-Week Post-Treatment visit.

The schedule of assessments is provided below. Details of the study procedures to be conducted for each subject enrolled in the study are presented in Study Procedures Table located in [Appendix 2](#). Information on the specific laboratory parameters to be measured and clinical assessments to be performed are provided in Section [6.4](#).

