#### **9.2.1. Analysis Sets**

##### 9.2.1.1. Efficacy

The analysis set for antiviral activity analyses will be the Full Analysis Set (FAS) which includes subjects with genotype 1, 2 or 3 HCV infection who were enrolled into the study and received at least one dose of study drug.

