### **9.4. Efficacy Analysis**

#### **9.4.1. Primary Analysis**

The primary efficacy endpoint is SVR12 (HCV RNA <LLOQ 12 weeks after cessation of therapy) in the FAS population.

The primary analysis will be performed after subjects have been followed through 12 weeks post-treatment or discontinued from study.

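### At the 120-day EMEA/AASLD cut, entry of Group 2 subjects to the SAP's full analysis set depends on outcome, so the Group 2 SVR12 rate is most likely biased low, by an amount the documents do not fix

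*Combined protocol and SAP*

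**What the plan says.** Protocol 9.2.1.1 defines an efficacy set that "includes subjects with genotype 1, 2 or 3 HCV infection who were enrolled into the study and received at least one dose of study drug". It sets no maturity condition. Protocol 9.4.1 times the primary analysis: "The primary analysis will be performed after subjects have been followed through 12 weeks post-treatment or discontinued from study".

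The SAP covers an earlier cut. Section 2.1 triggers it "After all group 1 and group 3 subjects" have reached post-treatment Week 12 or left the study, with a last-visit date of about 9 September 2013. Group 2 does not have to be mature, yet "an analysis will be conducted on key safety and efficacy data for all treatment groups".

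Section 3.1.1 then defines the FAS among enrolled and dosed subjects in two parts. The first is "Treatment-naive subjects with genotype 1, 2 or 3 HCV infection", without further condition. The second, for Group 2, is "Treatment-experienced subjects with genotype 2 or 3 infection who have completed the posttreatment Week 12 visit or prematurely discontinued from study".

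The SAP expects treated subjects to be left out. Section 3.6.1 gives imputation rules for subjects in the safety set but not in the FAS, and Section 6.2 and Listing 7.2 provide a listing for them. Under 3.1.1 these can only be Group 2 subjects.

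**The concern.** At a cut where part of Group 2 is immature, whether a subject counts depends on what has happened to that subject. A Group 2 subject who completes 24 weeks of treatment and keeps responding reaches post-treatment Week 12 at about Week 36. A subject of the same first-dose date who drops out meets the other limb of the rule on leaving and, without a post-treatment HCV RNA value, is a failure under SAP 3.6.1.

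Week 4 relapsers may behave in the same way. Protocol 6.3.1 sends only subjects below LLOQ at post-treatment Week 4 on to Week 12, and Protocol 6 states: "Completion of the study will occur at the 24-Week Post-Treatment visit". On that wording a relapser who leaves after Week 4 has not completed the study and can enter from about Week 28.

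The study is uncontrolled, so the SVR12 rate and its interval are the efficacy result for each group. The selected Group 2 set would feed the outcome table, the SVR and by-visit tables, the subgroup table and the forest plots. It would stand beside Groups 1 and 3, which are on an all-treated basis, under the same FAS label. The exact interval covers sampling error and not this selection.

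**Working it through.** **The plan's own precision figure.** SAP 1.3 gives Group 2 n = 55, expected SVR12 40% and a half-width of 12.9 points. The Wald half-width is 1.96 × √(0.40 × 0.60 / 55) = 0.1295, or 12.95 points, which agrees with the stated figure. The Clopper-Pearson interval planned for the analysis, at 22/55, runs from 13.0 points below to 14.1 points above. This is the scale against which to judge the bias.

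**Dates.** Counting back from 9 September 2013:
- 36 weeks (252 days) gives 31 December 2012. A Group 2 treatment completer first dosed later than this has not yet reached post-treatment Week 12.
- 28 weeks (196 days) gives 25 February 2013. Those first dosed between the two dates can already have relapsed at post-treatment Week 4.

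**Reading A: Week 4 relapsers are coded as prematurely discontinued.** Let p be the true SVR12 rate, m the share of Group 2 at or past Week 36 at the cut, and q the share of failures that leave the study before post-treatment Week 12. Suppose the immature subjects who will leave early have already left. The expected rate in the FAS is then

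m·p / [m + (1 − m)·q·(1 − p)].

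For q, protocol Table 1-5 (genotype 2/3 treatment-experienced, 12 weeks) shows 25 of 25 below detection at end of treatment, 19 at SVR4 and 17 at SVR12. So 6 of 8 failures (75%) appeared by Week 4. Applying this to Group 2 is an assumption.

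Worked case, p = 0.40, m = 0.8: 0.32 / (0.8 + 0.2 × 0.75 × 0.60) = 0.32 / 0.89 = 36.0%.

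| Immature share (1 − m) | True 40%, q = 75% | True 40%, q from 100% to 25% | True 68%, q = 75% | True 90%, q = 75% |
|---|---|---|---|---|
| 0 | 40.0% | 40.0% | 68.0% | 90.0% |
| 10% | 38.1% | 37.5-39.3% | 66.2% | 89.3% |
| 20% | 36.0% | 34.8-38.6% | 64.2% | 88.3% |
| 30% | 33.5% | 31.8-37.6% | 61.7% | 87.2% |
| 50% | 27.6% | 25.0-34.8% | 54.8% | 83.7% |

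The formula is on the high side for bias when immature subjects are recent, because some eventual failures have not yet left. A simulation allows for this (n = 55, 5% dropout, 75% of relapsers leaving at Week 30, immature subjects' first doses spread over 8 or 16 weeks). At a true 40% it gives 38.6% or 39.0% with 10% immature, 36.6% or 38.1% with 20%, and 32.4% or 35.5% with 40%. In the same runs, entry by first-dose date alone returned 39.8-40.1%.

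**Reading B: Week 4 relapsers are not coded as discontinued.** They have no Week 12 visit and meet neither limb of the rule, so they stay outside the FAS. If w is the share of failures of this kind, a fully mature Group 2 would show p / [p + (1 − p)(1 − w)]. With p = 0.40 and w = 0.60 this is 0.40 / (0.40 + 0.60 × 0.40) = 62.5%. A simulation with 60% Week 4 relapsers, 20% later failures and 20% early stops, and follow-up uniform from 12, 20 or 28 weeks up to 56 weeks, gives about 53% to 58%. These figures show direction; the documents do not support them as a forecast.

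**The case against.** The strongest objection is that the main driver is inferred. The SAP does not say when a Week 4 relapser counts as prematurely discontinued. Section 3.6.1 has rules for subjects outside the FAS whose SVR4 is a failure and for those who have completed the study, so it foresees some such subjects outside. This stands, and it is why the direction is given as most likely rather than certain. The protocol's definition of completion favours Reading A.

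A reader might infer that no Group 2 success can enter before Week 36, and that everyone entering by discontinuation is a failure. The documents do not support either. Protocol 7.2 keeps subjects in follow-up if they stop study drug with HCV RNA below LLOQ, so they can reach post-treatment Week 12 sooner. In SAP Table 3 the Week 12 window opens on day 70, and Section 3.7.2 uses all available HCV RNA, so a subject below LLOQ in that window who then leaves is a success. Both offset a downward bias; the early-stopper part is probably small.

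A reader might also take a loss of 5 to 10 points as established. That needs roughly 30-50% of Group 2 to be immature. Group 3 follows the same 36-week path and is mature at the cut, and nothing in the documents shows how far Group 2 accrual lagged.

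Finally, the SAP is partly transparent: it reports numbers per analysis set, counts still on study, and a listing of excluded subjects' HCV RNA. That discloses the exclusion but does not correct the rate or its interval.

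**Conclusion.** The point holds for this cut. Group 2 enters the FAS by an outcome-dependent rule at a time the plan allows it to be immature, and the set departs from the protocol's all-treated definition. If Week 4 relapsers are coded as discontinued, the Group 2 SVR12 rate is most likely biased low. If they are not, the bias could be upward.

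The size rests on unstated accrual. On Reading A it is zero if all Group 2 subjects were dosed by about 31 December 2012. With 10-20% immature and q = 75% it is about 2 to 4 points at a true 40%. With 30-50% immature it is 5 to 10 points or more, which is comparable with the planned half-width of 12.9 points. The zero case does not carry over to Reading B, where exclusion of relapsers persists as the group matures.

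A reader might infer that the trial's final result is compromised. It is not: this SAP governs only the 120-day/AASLD analysis, and Protocol 9.2.1.1 and 9.4.1 still define the final one on all treated subjects after full follow-up.

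**What to change.** In SAP 3.1.1, define the Group 2 efficacy set for this cut by first-dose date alone. Include every treated Group 2 subject dosed early enough that post-treatment Week 12 was due by the actual data cut, with an allowance for late visits, whatever the outcome or disposition. Count missing as failure.

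The allowance matters. The last-visit date is only approximate and the Week 12 HCV RNA window runs to day 146 after last dose, so a date set at the nominal visit would count late but in-window attenders as failures. Two options:
- Require the window to have closed. That is 24 × 7 + 146 = 314 days before 9 September 2013, or first dose by about 30 October 2012.
- Keep a later first-dose date and use in-window HCV RNA up to database finalization (about 30 September 2013). SAP 2.1 does not promise that data after the last-visit date are cleaned, so these HCV RNA records would need cleaning.

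Report the number of treated Group 2 subjects not yet eligible, and state how Week 4 relapsers are coded in disposition. Otherwise defer the Group 2 SVR12 estimate until all treated Group 2 subjects are mature.

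The cost is one sentence and one derivation flag, with a smaller early Group 2 denominator and a wider interval.

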##### **3.1.2. Safety Analysis Set**

The safety analysis set includes subjects who were enrolled and received at least one dose of study drug.

The safety analysis set will be used for all the analyses in the safety update except any efficacy analysis which will be based on the FAS and the summary of subject disposition which will be based on all screened subjects.

#### **3.2. Subject Groups**

All subjects will receive oral SOF 400 mg QD plus weight based RBV (1000 or 1200 mg/day) BID for 12 or 24 weeks, depending on genotype and prior treatment experience. Since this is an open-label study, it is unlikely that subjects could be enrolled into the wrong treatment group. Therefore, subjects will be grouped for analyses according to the treatment group they are enrolled into for all the analyses.

Specifically, subjects will be grouped into the following treatment groups for analyses:

Table 1.1: Treatment groups for efficacy analyses:

SOF+RBV 12 weeks			SOF+RBV 24 weeks					
Genotype 2/3 treatment-naive			Genotype 2/3 treatment-experienced			Genotype 1 treatment-naive		
Total	Genotype 2	Genotype 3	Total	Genotype 2	Genotype 3	Total	Genotype 1a	Genotype 1b

Table 1.2: Treatment groups for summary of demographics, disposition and exposure:

SOF+RBV 12 weeks			SOF+RBV 24 weeks					Grand Total
Total Genotype 2/3 treatment-naive	Genotype 2 treatment-naive	Genotype 3 treatment-naive	Total Genotype 2/3 treatment-experienced	Genotype 2 treatment-experienced	Genotype 3 treatment-experienced	Genotype 1 treatment-naive	Total of SOF+RBV 24 Weeks	

Table 1.3: Treatment groups for safety analyses:

SOF+RBV 12 weeks	SOF+RBV 24 weeks			Grand Total
Genotype 2/3 treatment-naive	Genotype 2/3 treatment-experienced	Genotype 1 treatment-naive	Total of SOF+RBV 24 weeks	

### 3.3. Strata and Covariates

There is no stratification in this study.

### 3.4. Examination of Subject Subsets

The efficacy endpoints SVR4 and SVR12 will be analyzed for the following subsets:

- age group on date of first dose of study regimen (< 50 years, ≥ 50 years )
- sex (male, female)
- race (black, non-black)

- ethnicity (hispanic or latino, non-hispanic or latino)
- cirrhosis(presence, absence)
- HCV genotype (1, 2, 3)
- baseline HCV RNA ( $< 6 \log_{10}$  IU/mL,  $\geq 6 \log_{10}$  IU/mL)
- baseline BMI ( $< 30 \text{ kg/m}^2$ ,  $\geq 30 \text{ kg/m}^2$ )
- baseline ALT ( $\leq 1.5 \times \text{ULN}$ ,  $> 1.5 \times \text{ULN}$ )
- IL28B (CC, non-CC)
- prior HCV treatment experience and response to prior HCV treatment (IFN-eligible treatment naive, IFN-ineligible treatment-naive, IFN intolerant, non-response, relapse/breakthrough)
- study drug completers and subjects who prematurely discontinued from drug
- ARV treatment experience at enrollment (untreated, treated)
- ARV regimen at enrollment

### **3.5. Data Handling Conventions and Transformations**

The COBAS® Taqman® HCV Test v2.0 for use with the High Pure System assay was used to determine HCV RNA results in this study. The lower limit of quantitation (LLOQ) of the assay is 25 IU/mL.

When the calculated IU/mL is within the linear range of the assay, then the result will be report as the “<< numeric value>> IU/mL”. This result will be referred to in this document as the numeric result or as “ $\geq$  LLOQ detected” for categorical result.

When HCV RNA is not detected, the result is reported as “HCV RNA not detected” or “target not detected”. This result will be referred to in this document as “< LLOQ target not detected” or “< LLOQ TND”.

When the calculated HCV RNA IU/mL is below LLOQ of the assay, the result is reported as “< 25 IU/mL, HCV RNA detected”. This result will be referred to in this document as “< LLOQ detected”.

For numerical HCV RNA data, values below LLOQ will be set to the LLOQ minus 1 (ie, 24 HCV RNA IU/mL). HCV RNA values returned as “target not detected” will also be set to 24 IU/mL.

For selected analyses, HCV RNA data (IU/mL) will be transformed to the logarithmic (base 10) scale ( $\log_{10}$  IU/mL).

Total bilirubin values entered as  $< 0.2$  mg/dL will be analyzed as 0.1 mg/dL; direct bilirubin values entered as  $< 0.1$  mg/dL will be analyzed as 0.05 mg/dL {20502}. In general, other than the above 2 exceptions, laboratory data that are continuous in nature but are less than the lower limit of quantitation or above the upper limit of quantitation will be imputed to the value of the lower or upper limit minus or plus 1 significant digit, respectively (eg, if the result of a continuous laboratory test is  $< 20$ , a value of 19 will be assigned).

### **3.6. Missing Data and Outliers**

#### **3.6.1. Missing Data**

A missing data point for a given study visit may be due to any one of the following reasons:

- A visit occurred but data were not collected or were unusable
- A visit did not occur
- A subject permanently discontinued from the study before reaching the window

For subjects in the FAS, missing HCV RNA data will only be imputed up to the posttreatment Week 12 visit, unless the subject has completed the study, his posttreatment Week 24 visit missing HCV RNA data will be imputed. HCV RNA data at posttreatment Week 24 visit will not be included in tables and figures, but will be listed.

For subjects in safety analysis set but not in FAS, missing HCV RNA data will not be imputed unless (1) it is preceded and followed in time by values which are not missing (i.e., bracketed). (2) the subject has completed the study. (3), SVR4 is a failure then SVR12 will be imputed as failure. No tables and figures will be generated for these subjects. Their HCV RNA data will be listed.

For analyses of categorical HCV RNA data, if a data point is missing and is preceded and followed in time by values that are “< LLOQ TND”, then the missing data point will be set to “< LLOQ TND”. If a data point is missing and preceded and followed by values that are “< LLOQ detected”, or preceded by “< LLOQ detected” and followed by “< LLOQ TND”, or preceded by “< LLOQ TND” and followed by “< LLOQ detected”, then the missing value will be set to “< LLOQ detected”; otherwise the data point will be termed a failure (ie,  $\geq$  LLOQ detected).

Subjects with missing data due to premature discontinuation of the study will have missing data imputed up to the time of their last dose (for on-treatment displays). If study days associated with the last dosing date is greater than the lower bound of a visit window, and the value at the visit is missing, then the value will be imputed. If the study days associated with the last dosing date is less than the lower bound of a visit window then the on-treatment value at that visit will remain missing.

If no HCV RNA values are obtained after the last dose of any study drug, the subject will be considered a treatment failure for SVR endpoints.

For the analyses of continuous HCV RNA efficacy data, any subject with a missing value in a visit window that is bracketed by prior and subsequent values of “< LLOQ TND” will be set to “< LLOQ TND” (ie, 24 IU/mL). Subjects with a missing data point preceded and followed by values that are “< LLOQ detected”, preceded by “< LLOQ detected” and followed by “< LLOQ TND”, or preceded by “< LLOQ TND” and followed by “< LLOQ detected” will be set to “< LLOQ detected” (ie, 24 IU/mL). No other imputation will be performed for continuous data.

Missing cirrhosis will be imputed as no cirrhosis.

Except for the imputation rules described above, values for other missing data (including all safety data) will not be imputed.

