- In the absence of a definitive diagnosis of presence or absence of cirrhosis by the above criteria, a liver biopsy is required during screening. If both a biopsy and FibroTest® plus APRI results are obtained, the biopsy results will supersede for the determination of cirrhosis.
- HIV antiretroviral therapy (ARV) criteria of one of the following:
  - ARV untreated for  $\geq 8$  weeks preceding the Screening visit with a CD4 T-cell count  $>500$  cells/mm^3 [up to 10% of study subjects may be ARV untreated], or
-

- 
- On a stable, protocol-approved, ARV for >8 weeks prior to Screening with a CD4 T-cell count >200 cells/mm^3 and undetectable plasma HIV-1 RNA level by local assay for  $\geq 8$  weeks preceding the Screening visit. HIV-1 viral load results should be measured within 1 year of the Screening visit. Screening HIV RNA must be < 50 cp/mL as measured by the COBAS AMPLIPREP/COBAS TaqMan 2.0 HCV RNA assay.
    - Subjects who switched from atazanavir/ritonavir (boosted) to darunavir/ritonavir (boosted) prior to Amendment 2 will be exempt from the 8 week stable ARV regimen requirement as defined in Section 6.4.2.
  - HIV antiretroviral medications allowed in this study include the following and should be administered per the prescribing information in the package insert:
    - emtricitabine/tenofovir plus:
      - atazanavir/ritonavir (boosted); or
      - darunavir/ritonavir (boosted); or
      - efavirenz; or
      - raltegravir; or
      - rilpivirine

Alternative combinations of the above listed medications may be allowed on a case by case basis. ARV regimens not on the above list are excluded from this study.

- Body mass index (BMI)  $\geq 18$  kg/m^2
  - Subjects must have the following laboratory parameters at Screening:
    - ALT  $\leq 10 \times$  the upper limit of normal (ULN)
    - AST  $\leq 10 \times$  ULN
    - Hemoglobin  $\geq 12$  g/dL for male,  $\geq 11$  g/dL for female subjects
    - INR  $\leq 1.5 \times$  ULN unless subject has known hemophilia or is stable on an anticoagulant regimen affecting INR
    - Albumin  $\geq 3$  g/dL
    - Direct bilirubin  $\leq 1.5 \times$  ULN
      - For subjects receiving an atazanavir/ritonavir (boosted) regimen, a direct bilirubin  $> 1.5 \times$  ULN will be allowed if <25% of the total bilirubin.
-

---

Diagnosis and Main  
Eligibility Criteria:  
(Continued)

- HbA1c  $\leq$  10%

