### 4.2. Inclusion Criteria

Subjects must meet *all* of the following inclusion criteria to be eligible for participation in this study.

1. Willing and able to provide written informed consent
2. Male or female, age  $\geq 18$  years with chronic HCV and HIV-1 infection
3. HCV RNA  $\geq 1 \times 10^4$  IU/mL at Screening
4. Infection with HCV genotype 1, 2 or 3 as determined at Screening
5. HIV-1 infection confirmed with positive ELISA and Western blot at Screening (if necessary)
6. The subject's medical records must be sufficient to be categorized on IFN eligibility or prior treatment with PEG/RBV into one of the following categories as defined in Section 6.4.2:

a) **Treatment Naïve - IFN-eligible**

b) **Treatment Naïve - IFN-ineligible:**

Subjects treated in the Drug Interaction portion (Part A) of the P7977-1910 protocol will be considered treatment-naïve.

c) **Treatment Experienced - IFN Intolerant (genotype 2/3 only)**

d) **Treatment Experienced - Non-Response (genotype 2/3 only)**

e) **Treatment Experienced - Relapse/Breakthrough (genotype 2/3 only)**

7. Confirmation of chronic HCV infection documented by either:
  - a positive anti-HCV antibody test or positive HCV RNA or positive HCV genotyping test at least 6 months prior to the Baseline/Day 1 visit, or

- a liver biopsy performed prior to the Baseline/Day 1 visit with evidence of chronic HCV infection
8. Ability to determine the presence/absence of cirrhosis
- a) Cirrhosis is defined as any one of the following:
- Liver biopsy within 2 years of screening showing cirrhosis
  - A FibroTest® score of >0.75 AND an AST:platelet ratio index (APRI) of >2 performed during screening
- b) Absence of cirrhosis is defined as any one of the following:
- Liver biopsy within 2 years of Screening showing absence of cirrhosis
  - A FibroTest® score of  $\leq 0.48$  AND APRI of  $\leq 1$  performed during Screening

In the absence of a definitive diagnosis of presence of cirrhosis by the above criteria, a liver biopsy is required.

If both a biopsy and FibroTest® plus APRI results are obtained, the liver biopsy results will supersede for the determination of cirrhosis.

9. HIV antiretroviral therapy (ARV) criteria of one of the following:
- a) ARV untreated, for  $\geq 8$  weeks preceding the Screening visit, with a CD4 T-cell count  $>500$  cells/mm^3 [up to 10% of study subjects may be ARV untreated], or

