### 6.1. Screening Assessments

#### 6.1.1. Screening Visit (Day -28 to Day 1)

Subjects will complete all screening assessments within 28 days of the Baseline/Day 1 visit. The screening window can be extended to 42 days for subjects requiring biopsy or in extenuating circumstances.

The following procedures will be performed and documented:

- Obtain signed informed consent
  - A separate informed consent will be required from subjects participating in the pharmacogenomic substudy.
- Obtain medical history
- Obtain information on prior HIV treatments
- Obtain information on IFN eligibility and prior treatment history with PEG-IFN as per Section [6.4.2](#). The following are the required source documents and medical information required for each of the defined criteria by genotype and treatment arm (redacted data to be provided to the sponsor prior to enrollment):
  - IFN Eligibility
    - Treatment naïve Genotype 1, 2 and 3
    - A redacted source document confirming IFN eligibility or ineligibility must be received and approved by the Sponsor/CRO prior to the subject being enrolled.

- IFN Intolerance
  - Treatment experienced Genotype 2 and 3 only
  - Start dates and stop dates for treatment with PEG-IFN (and RBV if applicable)
  - A redacted source document confirming IFN intolerance must be received and approved by the Sponsor/CRO prior to the subject being enrolled.
- Viral Response Data
  - Treatment experienced Genotype 2 and 3 only
  - In order to categorize the subject's prior response as either Non-Response or Relapse/Breakthrough, the following information must be provided to the Sponsor/CRO prior to enrollment:
    - Prior Treatment Dates (start and stop)
    - Prior Viral Response Data
    - HCV RNA assay
      - RT-PCR, TMA or bDNA
      - Undetectable as <LLOQ, BLOQ or <LLOD
- Cirrhosis determination as per Section 4.2
  - If the presence of cirrhosis is determined, then appropriate diagnostic imaging (CT or Ultrasound) should be performed to exclude the presence of hepatocellular carcinoma (HCC)
- Obtain details of concomitant medications and adverse events
- Perform complete physical examination including vital signs, body weight, and height.
- Perform 12-lead ECG
- Obtain blood samples for safety testing as well as:
  - HCV RNA
  - HIV RNA
  - CD4 T-lymphocyte Absolute Count and %
  - Determination of HCV viral genotype
  - HCV antibody, HIV 1/2 antibody, and HBs antigen

- HbA1c
- TSH
- IL28B

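### Missing cirrhosis status is imputed as no cirrhosis, although the protocol requires absence to be shown; the effect is confined to the baseline table and the cirrhosis subgroup rows

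*Combined protocol and SAP*

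**What the plan says.** SAP Section 3.6.1 (Missing Data): "Missing cirrhosis will be imputed as no cirrhosis". No reason is given. The sentence after it says that other missing data will not be imputed, so cirrhosis is the one baseline characteristic given an assumed value.

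The variable is used in two places. SAP Section 3.4 lists "cirrhosis(presence, absence" among the SVR4 and SVR12 subsets, which feed Table 6.1 and forest plots 3.1 and 3.2. SAP Section 5.1 puts it in the baseline table as yes/no. Neither place has an unknown level.

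Protocol Section 4.2, criterion 8, makes this an entry requirement: "Ability to determine the presence/absence of cirrhosis". The marker route to cirrhosis is a FibroTest "score of >0.75 AND an AST:platelet ratio index (APRI) of >2 performed during screening". Absence has its own definition ("Absence of cirrhosis is defined as any one of the following"): a biopsy within 2 years showing none, or FibroTest at or below 0.48 together with APRI at or below 1. For subjects meeting neither definition the Synopsis says: "In the absence of a definitive diagnosis of presence or absence of cirrhosis by the above criteria, a liver biopsy is required during screening". Section 4.2 says: "In the absence of a definitive diagnosis of presence of cirrhosis by the above criteria, a liver biopsy is required". Section 6.1.1 makes time for it: "The screening window can be extended to 42 days for subjects requiring biopsy or in extenuating circumstances".

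Protocol Section 9.2.2 limits imputation to the items discussed in that section. Cirrhosis is not among them.

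**The concern.** Under the protocol, not meeting the cirrhosis definition does not make a subject non-cirrhotic; absence needs its own evidence. The SAP rule drops that requirement for anyone whose status is missing. If status is missing because the markers were intermediate and no biopsy was done, the subject has failed the absence definition and is nevertheless tabulated as though it had been met.

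Two outputs are at stake. The non-cirrhotic SVR4 and SVR12 rows would include any true cirrhotics among the missing. The baseline table would understate the percentage with cirrhosis, which readers will compare with the planned figure of about 20%. Neither the tables nor the plots would show how many values were assumed.

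**Working it through.** **Step 1. The definitions side by side**

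| Evidence at screening | Protocol status | SAP status if recorded as missing |
|---|---|---|
| Biopsy showing cirrhosis, or FibroTest >0.75 and APRI >2 | Cirrhosis | Rule not reached |
| Biopsy showing none, or FibroTest ≤0.48 and APRI ≤1 | No cirrhosis | Rule not reached |
| Any other marker pair, no biopsy | Neither; biopsy required | No cirrhosis |
| Result lost or field not recorded | Unknown | No cirrhosis |

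The third line contradicts the protocol's definition. The fourth is an assumption with no evidence either way.

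**Step 2. The plan's own figures**

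The documents give no figure for missing cirrhosis status or for the precision of the cirrhosis rows. The only precision figures are the 95% half-widths in Protocol Section 9.8 and SAP Section 1.3. They reproduce with 1.96·√(p(1−p)/n):
- n = 55, p = 0.62: 12.8 points (stated 12.8)
- n = 55, p = 0.40: 12.9 points (stated 12.9)
- n = 115, p = 0.65: 8.7 points (stated 8.7)

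**Step 3. Size of the effect on the non-cirrhotic row**

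Inputs from the documents: about 20% cirrhotic, which gives 23 cirrhotic and 92 non-cirrhotic subjects in genotype 1 (n = 115), and 11 and 44 in each genotype 2/3 group (n = 55).

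Assumptions, not in the documents: SVR12 is lower in cirrhosis by g = 15 to 30 points; m = 1 to 10 subjects per group have missing status; a share f = 20% to 100% of them are truly cirrhotic; missingness is unrelated to response within each true status.

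With k = m·f true cirrhotics added to N non-cirrhotics, the row falls by g·k/(N + k).

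| Scenario | Genotype 1 (N = 92) | Each genotype 2/3 group (N = 44) |
|---|---|---|
| g = 15, k = 1 × 0.2 = 0.2 | 15 × 0.2/92.2 = 0.03 | 15 × 0.2/44.2 = 0.07 |
| g = 30, k = 5 × 0.5 = 2.5 | 30 × 2.5/94.5 = 0.79 | 30 × 2.5/46.5 = 1.61 |
| g = 30, k = 10 × 1.0 = 10 | 30 × 10/102 = 2.94 | 30 × 10/54 = 5.56 |

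The last line is an outer limit: it would leave 11 − 10 = 1 subject in the genotype 2/3 cirrhotic row.

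SAP Table 1.1 also splits the genotype 2/3 efficacy columns by genotype. With equal enrolment (27.5 per column) and 20% cirrhosis, each column has about 22 non-cirrhotic and 5.5 cirrhotic subjects. One misplaced cirrhotic then costs 30 × 1/23 = 1.3 points.

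**Step 4. An example in counts (assumed)**

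Take a group of 55 with 30/44 (68%) responding without cirrhosis and 4/11 (36%) with it, 34/55 (62%) in all. Let two true cirrhotics, both failures, have missing status.

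| | Non-cirrhotic row | Cirrhotic row | Group |
|---|---|---|---|
| True status | 30/44 = 68% | 4/11 = 36% | 34/55 = 62% |
| SAP rule | 30/46 = 65% | 4/9 = 44% | 34/55 = 62% |
| Missing shown separately | 30/44 = 68% | 4/9 = 44% | 34/55 = 62% |

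The baseline table would show 9/55 = 16.4% with cirrhosis, against a true 11/55 = 20.0%. A separate line of 2/55 = 3.6% not determined tells the reader that the true figure lies between 16.4% and 20.0%.

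**The case against.** The strongest reply is that the rule should rarely operate. Determinable status is an entry criterion, intermediate markers call for a biopsy, the biopsy overrides the markers, and screening can be lengthened to obtain it. A subject enrolled with undetermined status would be an eligibility deviation. The SAP says missing, not undetermined, and a lost or unrecorded result is as possible as an intermediate one. SAP Section 7.5 plans a listing of cirrhosis determination, although Appendix 1 gives it no separate title, and the HCV RNA listings in Section 6.2 carry cirrhosis status. The subgroup rows are descriptive, with no test or decision attached. All of this stands, and it limits the size of the problem. It does not justify the assigned value.

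A reader might infer three stronger things that the documents do not support.

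- *That the rule moves the subjects most likely to be cirrhotic.* Those subjects meet the biopsy or marker definition, are classified as cirrhotic and never reach the rule. What can be said is that a subject with intermediate markers has not met the absence definition.
- *That the rule is wrong every time it is used.* It is wrong only when the subject truly has cirrhosis; otherwise it is unsupported but correct.
- *That it flatters the results.* If cirrhotics respond less well, the non-cirrhotic rate goes down. The rise from 36% to 44% in the cirrhotic row occurs only because both moved subjects are assumed to be failures. With one success the row is 3/9 = 33%; with two it is 2/9 = 22%. The exact intervals are 11–69% for 4/11 and 14–79% for 4/9.

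The two biopsy sentences differ. The Synopsis refers to presence or absence, Section 4.2 to presence only. Both cover intermediate markers, so the difference does not by itself create missing status, but the wording should be reconciled.

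**Conclusion.** The point holds as a minor one. The SAP assigns a status that the protocol says must be shown, goes beyond the protocol's list of imputed items, gives no reason, and leaves no trace in the summary tables or plots.

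The consequence is contamination of the non-cirrhotic SVR4/SVR12 row and an understated percentage with cirrhosis, in both cases only to the extent that true cirrhotics are among the missing. With at most 5 missing per group, at most half of them cirrhotic, and a response gap of at most 30 points, the non-cirrhotic SVR12 falls by at most 0.8 points in genotype 1 and 1.6 points in each genotype 2/3 group. These sizes rest on assumed missingness and an assumed gap, since the documents report neither. With no missing status there is no effect. SVR12 by treatment group, the primary result, is unchanged in every scenario.

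**What to change.** Replace the sentence in SAP Section 3.6.1 with:

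> Subjects with missing cirrhosis status will be shown as 'not determined', with the count, in the baseline table and excluded from the cirrhosis present/absent rows of Table 6.1 and the forest plots; they remain in all other analyses.

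Add the third level to the cirrhosis entry in SAP Section 5.1. The SAP already accepts this kind of display: Section 7.1.2 shows unrecorded adverse event severity as missing.

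This removes the contamination of the non-cirrhotic row and makes the baseline table accurate about what is known. It does not return true cirrhotics to the cirrhotic row, as the last line of the counts example shows.

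The cost is one SAP sentence and one table level. No new data are needed. A few subjects may leave one subgroup display.
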